	Appendix C : EORTC QLQ-C30	

SCHEMA

M =	-26
11-	50

1.0 **OBJECTIVES**

1.1. Primary Objective:

- Progression free survival (PFS) at 4 months, as measured by Response Evaluation Criteria in Solid Tumors (RECIST).

1.2 Secondary Objectives:

- Objective response rate [compete response (CR), partial response (PR)]
- Clinical benefit [CR +PR + Stable disease ≥ 6 months]
- Assessment of toxicity
- Assessment of compliance with medication adherence
- Assessment of quality of life
- Assessment of bone health

1.3 Exploratory Objectives:

- Serial measurement of serum estradiol, estrone and estrone sulfate.

[figure not shown]
- To investigate treatment resistance (e.g. expression of amphiregulin, EGFR), using molecular

and immunohistochemical analyses of blood and tumor samples of preand post- (when available) treatment tissues. Microarraay analyses to quantitate the expression of specific estrogen-responsive genes (e.g. TTF1 and (PDZk1) will also be performed.

2.0 BACKGROUND AND RATIONALE

The efficacy of aromatase inhibitors (AI) in the treatment of postmenopausal women with hormone receptor positive, metastatic breast cancer (MBC) is undisputed. In this regard, prior randomized clinical trials have documented the superiority of exemestane (EXE) over tamoxifen, as first line therapy [1] and the superiority of EXE over megestrol acetate, as second line therapy after tamoxifen failure [2]. Prior phase II studies have also documented the efficacy of EXE in the treatment of MBC after failure of several lines of prior hormonal therapies [3], including prior exposure to nonsteroidal AIs [4, 5]. While the utility of EXE has been proven with respect to several important clinical indicators (e.g. response rate, time to progression, median survival time and median duration of response), eventually all patients will develop disease progression due to the development of acquired resistance to further treatment. In addition, as has recently been reported, some patients with breast cancer may derive less than maximal benefit from AI therapy due to noncompliance because of musculoskeletal-related adverse effects [6, 7]. The aim of this research proposal, therefore, is to determine whether there may be an effective strategy to delay the time to development of resistance to EXE in the treatment of MBC, while minimizing potential toxicities and ensuring patient compliance with treatment.

In order to achieve our study objectives, we propose a phase II pilot, translational trial incorporating the use of intermittent EXE therapy in the treatment of postmenopausal women with hormone receptor positive MBC. The rationale for this trial stems from preclinical data derived at the City of Hope, in the laboratory of our collaborator, [name] (Figure 1). As [name] research interests have been in identifying mechanisms of AI resistance, he has generated a unique research tool, MCF-7aro, an estrogen receptor positive breast cancer cell line in which aromatase is over-expressed [8,9]. Using this cell line, it was demonstrated that continuous exposure to EXE initially inhibited cell growth, indicative of the sensitivity of this cell line to treatment. With prolonged, continuous exposure to EXE, however, cells eventually resumed growth after 6-8 weeks of treatment, reflecting the gradual development of acquired resistance to further treatment. In contrast, in cells exposed to intermittent treatment with EXE, either on a schedule of 1 week on/1week off, 2 weeks on/1 week off or 3 weeks on/1 week off, sensitivity to growth inhibition by EXE was maintained beyond 12 weeks. These data suggest that the scheduling of EXE therapy may influence the clinical efficacy of this AI in the treatment of MBC.

While molecular mechanisms underlying this observation of delayed resistance are not yet fully elucidated, a clinical trial of intermittent EXE therapy in the treatment of MBC, is supported by both anecdotal clinical reports, as well as data derived from other laboratories. Clinical case reports have documented, for example, that patients with MBC can demonstrate regression of disease in response to withdrawal of antiestrogen treatments [10, 11]. This effect is presumed to result from of an adaptive hypersensitivity to low estrogen levels which over time, can lead to a paradoxical inhibitory effect of estrogen on breast cancer cell growth. A similar phenomenon has also been observed *in vitro* in that in LTED cells (i.e., MCF-7 breast cancer cells cultured under conditions of long-term estrogen deprivation), exposure to estrogen results in growth inhibition and induction of apoptosis [12]. In this regard, the current standard method of continuous daily dosing of EXE may not be as effective in inhibiting breast cancer cell growth, as sequencing intermittent periods of EXE

October 25, 2013

withdrawal. Moreover, in vitro and mouse xenograft models have shown that reversal of resistance to tamoxifen can be achieved with the administration of estrogen [13,14], suggesting that in patients with advanced, hormone receptor positive breast cancer, resistance to anti-estrogen therapy may possibly be delayed by allowing intermittent periods of exposure to low levels of estrogen. An alternative hypothesis to account for the development of acquired resistance to EXE is the recent finding of elevated expression of the epidermal growth factor (EGF)-like protein, amphiregulin (AREG), in MCF-7 aro cells treated continuously with 1µmol/L of EXE. As AREG binds to the EGF receptor, it is postulated that AREG may mediate the development of acquired resistance to EXE via activation of EGFR and MAPK, leading to cell proliferation. As such, it is possible that intermittent withdrawal of EXE may also delay the development of acquired endocrine resistance due to diminished expression of AREG [15]. In addition to the potential beneficial effects of intermittent EXE therapy in terms of prolongation of time to drug resistance, this new method of drug scheduling may also allow improvements of other clinically important endpoints, such as better quality of life due to reduced exposure to drug-related toxicities.

To correlate with observations obtained in cell culture (i.e. that intermittent EXE therapy delays the time to re-growth of MCF-7aro breast cancer cells), the selected primary endpoint of this study will be progression free survival (PFS), although other clinically meaningful endpoints, such as objective response rates and clinical benefit will also be measured. That PFS correlates with acquired resistance to treatment is exemplified by prior clinical trials in which it was shown that as first line therapy, median duration of response to EXE was reported as 10 months [1]. However, as second [2] and third [3] line therapies, time to tumor progression was reported as 20.3 weeks and 2 months, respectively. In other clinical trials in which EXE was used after multiple lines of prior endocrine therapy (≥ 2), including use of prior non-steroidal AIs, time to tumor progression ranged between 14.7 weeks to 3.7 months [4,5,16]. In view of these previously reported data and in consideration of the desire to be able to complete this study in a timely manner, we have chosen to measure PFS at 4 months as a benchmark for comparison (10 months for first line patients, see statistical considerations) and as such, have incorporated eligibility criteria to reflect the patient population from which these historical data were obtained [5,16]. The rationale for inclusion of this study population was also derived in consideration of the hypothesis that after long-term estrogen deprivation of hormone receptor positive breast cancer cells in vitro, (presumed to be clinically equivalent to long-term exposure to anti-estrogens), estrogen may actually induce apoptosis [12].

3.0 TREATMENT PLAN

3.1 Study Design

In order to test the study hypothesis that intermittent EXE may delay the time to development of acquired resistance, a pilot, phase II clinical trial will be conducted in which all study participants will receive treatment with EXE.

3.2 Treatment Dosage and Schedule

As is currently recommended, the standard approved dose of EXE is 25 mg orally per day, after a meal. Absorption of EXE is rapid, and after peak plasma levels are reached, plasma levels of EXE decline in a polyexponential manner, resulting in a terminal half life of approximately 24 hours. Given these pharmacokinetic properties and in consideration of convenience/ease of dosing, a 21-day treatment cycle, consisting of a schedule of 2 weeks on (consecutive daily dosing of 25 mg of EXE from Days 1-14), followed by 1 week off (cessation of dosing from Days 15-21), will be used.

3.3 Concurrent Treatment

Bisphosphonates

Concurrent bisphosphonates for the treatment of bone metastases will be permitted. In addition, throughout the study, concomitant medications deemed necessary for the supportive care of patients will be given at physician discretion.

Radiation

Subjects with measurable disease per RECIST criteria, who require palliative radiation to a non-target lesion, will be permitted to receive treatment without being considered as having disease progression. However, patients with measurable disease who require radiation to a target lesion will be considered as having disease progression and will be removed from study.

Subjects with non-measurable disease by RECIST criteria, who require palliative radiation to a single site, will be permitted to receive treatment and remain on study. However, subjects with non-measurable disease who required palliative radiation to more than one site will be considered as having disease progression and will be taken off study.

3.4 Number of Subjects

This trial will entail enrollment of a maximum of 36 patients for treatment, as discussed in section 6.0. The target accrual goal will be 18 subjects/year.

3.5 Treatment Duration and Follow-Up

Study subjects will remain on treatment until disease progression, the development

of unacceptable toxicities, consent withdrawal, PI discretion (in cases where further treatment on protocol would not be in the best interest of the study participant) or death. Study participants will be followed for one year after completion of study treatment.

4.0 SUBJECT ELIGIBILITY

4.1 Inclusion Criteria

- 4.1.1 Histologically or cytologically confirmed metastatic carcinoma of the breast.
- 4.1.2 Hormone receptor (ER and/or PR) positive disease [defined as: ER and/or PR positivity as ≥ 5% staining], as confirmed by immunohistochemistry (IHC) based on primary breast tissue or metastatic tissue.
- 4.1.3 Females \geq 18 years old and determined to be postmenopausal, as defined by any of the following:
 - Natural menopause, with at least one year since last menses.
 - Chemotherapy-induced menopause with at least 1 year from last menses and serum LH/FSH and estradiol levels within the postmenopausal range.
 - History of surgical or radiation-induced ovarian ablation.
 For women ≤ 56 years old and with a history of hysterectomy but at least one ovary intact, serum LH/FSH and estradiol levels must be within the postmenopausal range.
- 4.1.4 Postmenopausal women with disease recurrence while receiving either tamoxifen or a non-steroidal AI as adjuvant therapy (as long a adjuvant hormonal therapy was taken for 6 months before disease progression) or with disease recurrence following the discontinuation/ completion of adjuvant hormonal therapy.
- 4.1.5 Postmenopausal women with disease progression following either 0, 1 or 2 prior hormonal therapies for metastatic breast cancer, as long as subject has had no prior exposure to EXE.
- 4.1.6 Measurable or non-measurable (but evaluable) disease, as defined by RECIST criteria.
- 4.1.7 ECOG performance status (Appendix B) of 0-1 and adequate hematologic (neutrophil count $\geq 1.5 \times 10^9$ cells/L; platelet count $\geq 100 \times 10^9$ cells/L), renal (serum creatinine ≤ 1.5 times the upper limit of normal) and hepatic (total serum bilirubin ≤ 1.5 times the upper limit of normal; AST/ALT levels ≤ 2.5 times the upper limit of normal in patients without liver metastases or ≤ 5 times the upper limit of normal in patients with liver metastases; alkaline phosphatase ≤ 2.5 times the upper limit of normal for patients without bone or liver metastasis) function.
- 4.1.8 Subjects must have an estimated life expectancy of greater than 6 months.

4.2 Exclusion Criteria

- 4.2.1 Prior exposure to EXE, whether in the adjuvant or metastatic setting.
- 4.2.2 Prior history of any other cancer with the exception of non-melanoma skin cancer and treated *in situ* carcinoma of the cervix.
- 4.2.3 Active or symptomatic CNS metastasis (stable or treated brain metastasis allowed but patients must be off decadron, if given for CNS disease).
- 4.2.4 Hormone receptor negative or unknown breast cancer.
- 4.2.5 More than two prior chemotherapy regimen for treatment of metastatic disease (any prior chemotherapy given in the adjuvant setting is permitted).
- 4.2.6 Administration of any other anti-cancer therapy within 2 weeks of initiating study treatment. Use of bisphosphonates, however, are permitted for patients with known bone metastases.
- 4.2.7 Treatment with any other concurrent investigational agent or antitumor drug (chemotherapy, antibody therapy or other biologic agents), will not be permitted.
- 4.2.8 Any uncontrolled medical co-morbidity or psychiatric disorder which interferes with the ability to provide informed consent or comply with study procedures.

4.3 Minorities and Women Statement

Female subjects of all racial/ethnic groups are eligible for this study if they meet the eligibility criteria specified in sections 4.1 and 4.2. To address disparities in healthcare and breast cancer treatment among women from underserved populations, all efforts will be made to accrue subjects from ethnically diverse, underserved and minority populations. In order to achieve this goal, this study will be conducted with the collaboration of [name] who has established the City of Hope Center of Community Alliance for Research and Education (CCARE), an organization charged with increasing the awareness of cancer clinical trials among underserved populations.

5.0 STUDY PROCEDURES

5.1 Screening

A signed and dated IRB approved protocol consent form must be obtained before any study specific procedures can be performed. Procedures that are considered part of routine care are not considered study specific procedures but may be used to determine eligibility during screening. The following assessments must be performed within 28 days of initiation of treatment:

- Review of inclusion and exclusion criteria.
- Recording of concomitant mediation, including date of last use of prior therapy for treatment of breast cancer.
- Complete review of medical history (documentation of diagnosis, hormone receptor status of tumor, most recent radiologic assessment of disease status and prior treatment history)
- Complete physical examination, including assessment of ECOG performance status.
- Laboratory assessment for hematologic, renal and hepatic function.
- Disease assessment according to RECIST criteria. All baseline radiologic scans (CT, MRI, bone scans) must be performed within 28 days of study initiation. [*Note: PET/CT Scan may be used in lieu of Bone Scan when patient is symptomatic*]
- If available, submission of archival paraffin-embedded or fresh frozen tumor tissue samples.

5.2 Tumor Assessments

Radiologic assessment of disease must include computed tomography (CT) or magnetic resonance imaging (MRI) of the chest, abdomen and pelvis and the imaging modality selected should remain consistent throughout the entire study. All subjects will additionally undergo a bone scan at baseline *[Note: PET/CT Scan may be used in lieu of Bone Scan when patient is symptomatic]*. Subjects with a positive bone scan at baseline will continue to have bone scans as part of their radiologic assessments throughout the study period. Subjects with a negative bone scan at baseline, will not be required to continue with further bone scans during the study period, unless clinically indicated. All imaging studies will be required at baseline and will be repeated every 3 cycles (i.e. day 15-21 of every 3rd cycle). Tumor response assessments will be performed according to RECIST criteria:

Response Evaluation Criteria in Solid Tumors (RECIST) Quick Reference

Eligibility

Measurable disease - the presence of at least one measurable lesion. If the measurable disease is restricted to a solitary lesion, its neoplastic nature should be confirmed by cytology/histology.

Measurable lesions - lesions that can be accurately measured in at least one dimension with longest diameter ≥ 20 mm using conventional techniques or ≥ 10 mm with spiral CT scan.

Non-measurable lesions - all other lesions, including small lesions (longest diameter <20 mm with conventional techniques or <10 mm with spiral CT scan), i.e., bone lesions, leptomeningeal disease, ascites, pleural/pericardial effusion, inflammatory breast disease,

lymphangitis cutis/pulmonis, cystic lesions, and also abdominal masses that are not confirmed and followed by imaging techniques.

- All measurements should be taken and recorded in metric notation, using a ruler or calipers. All baseline evaluations should be performed as closely as possible to the beginning of treatment and never more than 4 weeks before the beginning of the treatment.
- The same method of assessment and the same technique should be used to characterize each identified and reported lesion at baseline and during follow-up.
- Clinical lesions will only be considered measurable when they are superficial (e.g., skin nodules and palpable lymph nodes). For the case of skin lesions, documentation by color photography, including a ruler to estimate the size of the lesion, is recommended.

Methods of Measurement

- CT and MRI are the best currently available and reproducible methods to measure target lesions selected for response assessment. Conventional CT and MRI should be performed with cuts of 10 mm or less in slice thickness contiguously. Spiral CT should be performed using a 5 mm contiguous reconstruction algorithm. This applies to tumors of the chest, abdomen and pelvis. Head and neck tumors and those of extremities usually require specific protocols.
- Lesions on chest X-ray are acceptable as measurable lesions when they are clearly defined and surrounded by aerated lung. However, CT is preferable.
- When the primary endpoint of the study is objective response evaluation, ultrasound (US) should not be used to measure tumor lesions. It is, however, a possible alternative to clinical measurements of superficial palpable lymph nodes, subcutaneous lesions and thyroid nodules. US might also be useful to confirm the complete disappearance of superficial lesions usually assessed by clinical examination.
- The utilization of endoscopy and laparoscopy for objective tumor evaluation has not yet been fully and widely validated. Their uses in this specific context require sophisticated equipment and a high level of expertise that may only be available in some centers. Therefore, the utilization of such techniques for objective tumor response should be restricted to validation purposes in specialized centers. However, such techniques can be useful in confirming complete pathological response when biopsies are obtained.
- Tumor markers alone cannot be used to assess response. If markers are initially above the upper normal limit, they must normalize for a patient to be considered in complete clinical response when all lesions have disappeared.

• Cytology and histology can be used to differentiate between PR and CR in rare cases (e.g., after treatment to differentiate between residual benign lesions and residual malignant lesions).

Baseline documentation of "Target" and "Non-Target" lesions

- All measurable lesions up to a maximum of five lesions per organ and 10 lesions in total, representative of all involved organs should be identified as *target lesions* and recorded and measured at baseline.
- Target lesions should be selected on the basis of their size (lesions with the longest diameter) and their suitability for accurate repeated measurements (either by imaging techniques or clinically).
- A sum of the longest diameter (LD) for *all target lesions* will be calculated and reported as the baseline sum LD. The baseline sum LD will be used as reference by which to characterize the objective tumor.
- All other lesions (or sites of disease) should be identified as *non-target lesions* and should also be recorded at baseline. Measurements of these lesions are not required, but the presence or absence of each should be noted throughout follow-up.

Response Criteria

Evaluation of target lesions

* Complete Response (CR):	Disappearance of all target lesions	
* Partial Response (PR):	At least a 30% decrease in the sum of the LD of target lesions, taking as reference the baseline sum LD	
* Progressive Disease (PD):	At least a 20% increase in the sum of the LD of target lesions, taking as reference the smallest sum LD recorded since the treatment started or the appearance of one or more new lesions	
* Stable Disease (SD):	Neither sufficient shrinkage to qualify for PR nor sufficient increase to qualify for PD, taking as reference the smallest sum LD since the treatment started	
	Evaluation of non-target lesions	
* Complete Response (CR):	Disappearance of all non-target lesions and normalization of tumor marker level	
* Incomplete Response/ Stable Disease (SD):	Persistence of one or more non-target lesion(s) or/and maintenance of tumor marker level above the normal limits	
* Progressive Disease	Appearance of one or more new lesions and/or unequivocal	
3 #08063	13 October 25, 2013	

(1) Although a clear progression of "non target" lesions only is exceptional. In such circumstances, the opinion of the treating physician should prevail and the progression status should be confirmed later on by the review panel (or study chair).

Evaluation of best overall response

(PD):

The best overall response is the best response recorded from the start of the treatment until disease progression/recurrence (taking as reference for PD the smallest measurements recorded since the treatment started). In general, the patient's best response assignment will depend on the achievement of both measurement and confirmation criteria

Target lesions	Non-Target lesions	New Lesions	Overall response
CR	CR	No	CR
CR	Incomplete response/SD	No	PR
PR	Non-PD	No	PR
SD	Non-PD	No	SD
PD	Any	Yes or No	PD
Any	PD	Yes or No	PD
Any	Any	Yes	PD

- Patients with a global deterioration of health status requiring discontinuation of treatment without objective evidence of disease progression at that time should be classified as having "symptomatic deterioration". Every effort should be made to document the objective progression even after discontinuation of treatment.
- In some circumstances it may be difficult to distinguish residual disease from normal tissue. When the evaluation of complete response depends on this determination, it is recommended that the residual lesion be investigated (fine needle aspirate/biopsy) to confirm the complete response status.

Confirmation

• The main goal of confirmation of objective response is to avoid overestimating the response rate observed. In cases where confirmation of response is not feasible, it should be made clear when reporting the outcome of such studies that the responses are not confirmed.

- To be assigned a status of PR or CR, changes in tumor measurements must be confirmed by repeat assessments that should be performed no less than 4 weeks after the criteria for response are first met. Longer intervals as determined by the study protocol may also be appropriate.
- In the case of SD, follow-up measurements must have met the SD criteria at least once after study entry at a minimum interval (in general, not less than 6-8 weeks) that is defined in the study protocol

Duration of overall response

• The duration of overall response is measured from the time measurement criteria are met for CR or PR (whichever status is recorded first) until the first date that recurrence or PD is objectively documented, taking as reference for PD the smallest measurements recorded since the treatment started.

Duration of stable disease

• SD is measured from the start of the treatment until the criteria for disease progression are met, taking as reference the smallest measurements recorded since the treatment started.

5.3 Toxicity Assessments

To protect against and minimize potential risks, assessments of treatment-related toxicities will be performed by the study nurse every three weeks (via telephone). The NCI, Common Toxicity Criteria for Adverse Events (CTCAE, version 3.0, available at http://ctep.cancer.gov//forms/CTAEv3.pdf)), will be used as a guide to assess severity. To assess musculoskeletal adverse effects associated with EXE use, all subjects will complete modified Health Assessment Questionnaires (HAQ DI©) (Appendix A) at the start of each cycle of treatment, as previously validated [7, 17].

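### Section 5.2 lets a lesion irradiated shortly before entry serve as a RECIST target, so radiation shrinkage after the baseline scan can delay progression or add to a response

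*Combined protocol and SAP*

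**What the plan says.** - **Target selection (5.2, baseline documentation of lesions).** The rule covers "All measurable lesions up to a maximum of five lesions per organ and 10 lesions in total". It adds that "Target lesions should be selected on the basis of their size (lesions with the longest diameter) and their suitability for accurate repeated measurements". Prior radiation is not a criterion.
- **Measurable lesion (5.2).** These are "lesions that can be accurately measured in at least one dimension with longest diameter" at or above 20 mm by conventional techniques or 10 mm by spiral CT. Bone lesions are listed as non-measurable; irradiated lesions are not.
- **Washout (4.2.6).** The exclusion is "Administration of any other anti-cancer therapy within 2 weeks of initiating study treatment". Radiation is not named.
- **Baseline scan.** Section 5.1 says that baseline scans "must be performed within 28 days of study initiation". Section 5.2 asks for baseline evaluation as near to the start as possible and "never more than 4 weeks before the beginning of the treatment".
- **Radiation on study (3.3).** Here "patients with measurable disease who require radiation to a target lesion will be considered as having disease progression", and they leave the study. Nothing corresponds to this for radiation before Day 1.
- **Data collected (5.1).** Prior treatment history and the date of last prior therapy are recorded per subject. No item identifies which lesion was irradiated.
- **Use of the sum (5.2, 6.1).** PR is "At least a 30% decrease in the sum of the LD of target lesions" from baseline. PD is a 20% rise from the smallest sum recorded, or a new lesion. Primary success is being progression-free at 4 months, or at 10 months for first-line subjects.

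**The concern.** The baseline scan window (28 days) is longer than the washout (14 days). A lesion can be measured on Day -28, irradiated on Days -25 to -15, and enter the baseline sum at its pre-radiation diameter, all within the protocol. A scan taken soon after radiation has the same problem if the lesion is still shrinking.

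In either case the later fall in that lesion is counted as if it happened under exemestane. It can offset growth elsewhere in the sum, and so delay PD, or help the sum reach the PR threshold. The trial has one arm, so no control group carries the same error, and the error at entry and at the first scan favours the regimen. The endpoints exposed are the primary success count, the response rate and clinical benefit.

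**Working it through.** **Plan's own figures.** The lesion rule has no stated figure. The two-stage design in 6.1 (stop if fewer than 6 of 21 succeed; promising if at least 14 of 36 do) reproduces by exact binomial calculation:

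| Quantity | Stated | Recomputed |
|---|---|---|
| Early stopping, true rate 30% | 36% | 36.3% |
| Early stopping, true rate 50% | 1% | 1.3% |
| Type I error | under 17% | 15.97% |
| Type II error | 7% | 6.97% |

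None of these depends on how lesions are classified.

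**Inputs for the illustration.** The PD threshold (+20% from the smallest sum) and the PR threshold (-30% from baseline) come from 5.2. The lesion sizes and shrinkages are assumed. There are two targets of diameter 1, so the baseline sum is 2, and the baseline sum is the PD reference until a lower one is recorded. The irradiated lesion shrinks by a fraction *s* after the baseline scan and then stays there. The other lesion grows by *g* from baseline.

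**First on-study scan (week 9).** PD needs (1 - *s*) + (1 + *g*) ≥ 1.2 × 2 = 2.4, so *g* ≥ 0.4 + *s*.

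**Later scan, after a lower sum has been recorded.** Let the other lesion have grown by *h* at the first scan. The recorded sum is 2 + *h* - *s*. PD needs (1 - *s*) + (1 + *g*) ≥ 1.2 × (2 + *h* - *s*), so *g* ≥ 0.4 + 1.2*h* - 0.2*s*.
- *h* = 0: *s* = 0.3 gives 0.4 - 0.06 = 0.34; *s* = 0.5 gives 0.4 - 0.10 = 0.30.
- *h* = 0.2: *s* = 0.3 gives 0.4 + 0.24 - 0.06 = 0.58; *s* = 0.5 gives 0.4 + 0.24 - 0.10 = 0.54.

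Growth of the non-irradiated lesion needed for PD by target sum:

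| The other lesion | First scan | Later, if unchanged at first scan | Later, if +20% at first scan |
|---|---|---|---|
| Not a target | 20% | 20% | PD already |
| Target, stable | 40% | 40% | 40% |
| Target, shrinks 30% | 70% | 34% | 58% |
| Target, shrinks 50% | 90% | 30% | 54% |

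The step from 20% to 40% is ordinary dilution by any stable second target. The part due to radiation at the first scan is the step from 40% to 70% or 90%.

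**Response.** If the irradiated lesion is the only target, a 30% shrinkage meets the PR threshold. With a 60 mm irradiated lesion that halves and a 40 mm lesion unchanged, the sum goes from 100 to 70 mm (-30%, PR threshold met). With two equal 40 mm lesions, halving one gives 80 to 60 mm (-25%, stable disease); it takes 60% shrinkage (80 to 56 mm) to reach -30%.

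**Sensitivity of the decision rule (assumed frequency).** Suppose masking lasts until the success evaluation and adds one expected false success in 36 at a true rate of 30%. The rate becomes 0.30 + 1/36 = 0.328, and the chance of calling the regimen promising rises from 16.0% to 26.5%. With two (0.356) it is 39.2%. These figures show only how sensitive the rule is; they do not estimate how often masking occurs.

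**The case against.** The best case for leaving the text alone has several parts.

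- **The PD reference falls with the sum.** This stands. The 70% and 90% figures apply only until a lower sum is recorded. If the other lesion was unchanged at that scan, the requirement drops to 34% or 30%, which is easier to meet than the 40% with a stable second target. It does not remove the problem when the other lesion was already growing at the first scan (54% to 58% against 40%).
- **Other routes to PD and a check on PR remain.** This stands. New lesions and unequivocal non-target progression still give PD, bone lesions are never targets, and PR needs confirmation at 4 weeks or later. A lasting radiation effect could still pass confirmation.
- **The scan-then-radiation sequence is constructed.** This stands in part. Section 5.2 prefers a scan near the start, and 28 days is an outer limit, but the sequence is allowed.
- **The section is a quick reference.** Whether the full criteria deal with irradiated lesions cannot be checked from these documents. The rules reproduced for sites do not.

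A reader might infer more than the text supports:
- That every irradiated lesion has to be a target. The rule says should, has caps, and asks for suitability for repeat measurement. Below the caps, though, nothing keeps the lesion out.
- That any radiation shrinkage before entry distorts the sum. Shrinkage complete at the baseline scan only sets a lower reference.
- That 3.3 contradicts 5.2. Section 3.3 governs radiation needed on study, as a sign of treatment failure; it does not address whether a lesion irradiated earlier is a valid measurement.

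**Conclusion.** The gap is real and worth correcting. As written, a measurable lesion irradiated before entry can be a target, and any radiation shrinkage after its baseline scan can delay PD or contribute to a PR.

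In the two-lesion illustration the growth needed for PD at the first on-study scan is 70% or 90%, against 40% with a stable second target. After a lower sum is recorded with the other lesion unchanged, it is 34% or 30%.

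This rests on assumed lesion sizes and shrinkages, and on reading radiation as anti-cancer therapy in 4.2.6. If that reading is wrong, the protocol has no washout for radiation and the gap is wider. The number of affected subjects cannot be derived from the documents, so the effect on the trial's success count is unknown. It would be wrong to conclude that the stated error rates are miscalculated: they reproduce, and the fix does not change them.

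**What to change.** Add to the baseline lesion rules in 5.2: *A lesion irradiated before study entry is recorded as non-target, unless growth after the end of radiation is documented and its baseline measurement comes from a scan taken after radiation ended.* Add to the baseline form, for each lesion, prior radiation (yes/no) and end date. State in 4.2.6 whether radiation is covered.

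**Cost.** One sentence, one form item and one clarification. Accrual is not reduced, because 4.1.6 already admits non-measurable disease.

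**Downsides to state in the protocol.** Some lesions move to non-target, and a subject whose measurable lesions are all reclassified becomes non-measurable. For those lesions PD rests on unequivocal progression, which relies more on physician judgement. Subjects left without a target cannot score PR by target sum. Section 3.3 also handles on-study radiation differently for target lesions, non-target lesions and non-measurable subjects, so reclassification can change who is declared progressed. Sections 5.2 and 3.3 need to be reconciled for these subjects; which radiation rule should apply is for the sponsor and investigators to decide.
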